10 DEVIATIONS FROM THE CLINICAL INVESTIGATION PLAN

Since this is a post-marketing clinical follow-up observational study, based in a real-life setting, no major deviations from the CIP are expected.

11 DEVICE ACCOUNTABILITY

Not applicable, as the product is commercialized (per Annexe I, clause 7 d) 1) of the EN ISO 14155 2020).

The investigator must ensure that the patients' parents or legal guardians understand the objectives of this investigation and the ICF before signing it and that they understand that the device can only be used in the patient who has been enrolled in the investigation.

In the event of a device deficiency or an adverse device effect, all details will be recorded by the parent/legal guardian in the mobile application, after which a notification will be sent to the Investigator and the data service provider (CEN). Contact will be established with the user as soon as possible by the Investigator, who will confirm the event details.

12 STATEMENTS OF COMPLIANCE

12.1 General statements of compliance

The current versions of the Guidelines of the World Medical Association's Declaration of Helsinki, EN ISO 14155 standard as well as demands of the national and European medical product laws and data protection laws (such as the GDPR) will be implemented and followed.

Compliance with these standards will ensure that the rights, safety and well-being of study subjects are protected and that data from the clinical investigation are of the highest quality standards.

All clinical work conducted under this protocol will be subject to GCP (Good Clinical Practice). The Investigator must agree to the inspection of investigation-related documents and records by health authorities, auditors and/or the sponsor or its designee upon request.

In accordance with national provisions, the start of the investigation is notified immediately (i.e. as soon as the sponsor or his representative in charge of the clinical investigation becomes aware of it) to the CPP and ANSM (*Agence Nationale de sécurité du médicament et des produits de santé*) by email until EUDAMED is made available. The effective date of the start of the clinical investigation corresponds to the date of signature of the consent form of the first person who agrees to the clinical investigation in France.

A notification of the end of the study will be sent within 15 days following the end of the clinical investigation, or its temporary interruption or its early termination to the authorities.

The summary and the clinical report will be transmitted according to the local regulation within 1 year after the end of the clinical investigation or within 3 months following the temporary interruption or early termination.

The sponsor has been informed that the competent authority (ANSM) may contact the CPP which is reviewing or which has reviewed the authorization and opinion application file for this clinical investigation.

This clinical investigation conducted under Article 82 of Regulation (EU) 2017/745 which is not subject to an insurance obligation.

The data recorded during this research is subject to computerized processing at CEN, responsible for the implementation of data processing in compliance with Regulation (EU) 2016/679 of the European Parliament and of the Council relating thereto. to the protection of individuals with regard to the processing of personal data and the free movement of such data and law n°78-17 of 6 January 1978 relating to data processing, files and freedoms, as amended by law 2018-493 of June 20, 2018.

This research is part of the "Reference Methodology" (MR-001) pursuant to the provisions of Article 54 paragraph 5 of the amended law of January 6, 1978 relating to information, files and freedoms. This change was approved by decision of January 5, 2006, updated on July 21, 2016. CEN has signed a commitment to comply with this "Reference Methodology".

The secure data collection application on smartphone NursTrial® has specific security and anonymization measures.

Pending the European database EUDAMED, this clinical investigation is registered under number ID-RCB: 2023-A01929-36.

12.2 Ethics and Regulatory Authority approval

Prior to study initiation, the CIP, sample ICF and the data collection tools will be submitted to the National Ethics Committee (Comité de Protection des Personnes – CPP – in France) for review and approval and the national competent authority (ANSM) for approval of the submitted file.

The clinical investigation will not begin until all necessary approvals/favourable opinions are obtained from the CPP and the regulatory authorities. Should the CPP and authorities impose any additional requirements, they will be duly implemented.

The sponsor and/or designee will keep on file records of approval of all documents pertaining to this study.

12.3 Financing

The costs associated with the clinical investigation and investigator/site compensation will be documented in a separate agreement that will be signed by the sponsor, the investigator and/or the management of the study site.

13 INFORMED CONSENT PROCESS

The parent(s) or legal guardian of each patient will be provided with oral (overall presentation of the study by the pharmacist) and written information in lay and native language which describes:

- The objective, nature, advantages, consequences, risks and disadvantages of the clinical investigation, the constraints, the foreseeable risks and the expected benefits of the clinical investigation;
- The rights and guarantees of the patient concerning his protection, in particular his right to refuse to participate in the clinical investigation and his right to withdraw from it at any time without incurring prejudice and without having to justify himself, and specifies the rights of the patient in the context of a clinical trial on the medical device;
- The conditions under which the clinical investigation must take place, including the planned duration of the participation of the person concerned, including the follow-up measures if the participation is terminated;
- Information relating to the identification of the clinical investigation, and the availability of results.

Each subject will be given a paper copy of the information note and of the informed consent content by the pharmacist at pre-screening step, and will encourage to carefully read this information note prior the remote visit with the Investigator.

In this clinical investigation conducted in young children, to comply with the French Public Health Code regarding the assent of the children able to understand their participation to the study, a dedicated information note will be given to the parent/legal representative. The investigator will read the letter to the child if applicable.

It is the responsibility of the Investigator to explain the details of the investigation to the subject's parent(s)/legal guardian. The Investigator or the delegated doctor/health professional answers all of the questions of the patient's parent/legal representative and ensures that he/she has understood the information and explanations provided. The patient's parent/legal representative is given the necessary duration to provide their decision to participate in the clinical investigation.

If the patient's parent/legal representative agrees to participate, the Investigator and the patient's parent/legal representative proceed to the electronic signature of the informed consent (ICF).

Before any procedures related to the research, the investigator must obtain the free, informed and written consent of the patient's parent/legal representative.

Consent will be electronically signed using a solution (*DocuSign*) whose functionality meets recommended expectations of the Guidance on computerized systems and electronic data in clinical trials (EMA/INS/GCP/112288/2023). Briefly, the system will include functionality to:

- authenticate the signatory;
- ensure non-repudiation;
- ensure an unbreakable link between the electronic record and its signature;
- provide a timestamp.

In this clinical investigation, a double level of authentication will be used (personal email and phone number). Then, the patient's parent/legal representative will receive an email with a link to access to the electronic ICF and proceed to signature after confirmation of having read the ICF.

Once signed by the patient's parent/legal representative and the Investigator, both received an electronic ICF specifying date and time for signature. The Investigator will document the signature in the e-CRF, and stored the e-ICF in the dedicated study file.

In the event that an amended ICF is implemented, it must be reviewed and signed by the subject's party and the investigator in the same way as the original consent.

The subject will not be included in the investigation under any circumstance if his/her parent(s) or legal guardian did not provide their informed consent.

14 MANAGEMENT AND REPORTING OF ADVERSE EVENTS, ADVERSE DEVICE EFFECTS AND DEVICE DEFICIENCIES

14.1 Definitions

A qualified and suitably trained medical professional will assess all declared adverse events (AE) and adverse device effects (ADE), that would be reported by the patient/parents during the 3 days of using Petit Drill.

All definitions are issued from REGULATION (EU) 2017/745 OF THE EUROPEAN PARLIAMENT AND OF THE COUNCIL of 5 April 2017 on medical devices, and corresponding Medical Device Coordination Group (MDCG) guidelines.

14.1.1 *Adverse Event (AE) - Article 2 (57) from MDR*

Any untoward medical occurrence, unintended disease or injury or any untoward clinical signs including an abnormal laboratory finding, in subjects, users or other persons, in the context of a clinical investigation, whether or not related to the investigational device.

Note 1: This includes events related to the study product (including test product and/or associated products) and/or related to the procedures involved (any procedure in the clinical investigation plan).

Note 2: For users or other persons this is restricted to events related to the investigational medical device.

Note 3: An Adverse Device Effect (ADE) is an AE related to the use of the investigational medical device.

14.1.2 *Serious Adverse Events (SAE) - Article 2 (58) from MDR*

Any adverse event that led to any of the following:

- (a) death,
- (b) serious deterioration in the health of the subject that resulted in any of the following:
 - (i) life-threatening illness or injury,
 - (ii) permanent impairment of a body structure or a body function,
 - (iii) hospitalisation or prolongation of patient hospitalisation,
 - (iv) medical or surgical intervention to prevent life-threatening illness or injury or permanent impairment to a body structure or a body function,
 - (v) chronic disease.
- (c) foetal distress, foetal death or a congenital physical or mental impairment or birth defect.

Note 1: A planned hospitalisation for pre-existing condition, or a procedure required by the protocol, without a serious deterioration in health, is not considered to be a serious adverse event.

Note 2: This also includes device deficiencies that might have led to a SAE if a) suitable action had not been taken or b) intervention had not been made or c) if circumstances had been less fortunate.

A Serious Adverse Device Effect (SADE) is an AE related to the use of an investigational medical device and leading to the situations described above for SAEs.

14.1.3 *Device deficiencies (DD) - Article 2 (59)*

Any inadequacy in the identity, quality, durability, reliability, safety or performance of an investigational device, including malfunction, use errors or inadequacy in information supplied by the manufacturer.

14.1.4 *Incident – Article 2 (64)*

Any malfunction or deterioration in the characteristics or performance of a device made available on the market, including use-error due to ergonomic features, as well as any inadequacy in the information supplied by the manufacturer and any undesirable side-effect.

14.1.5 *Serious incident – Article 2 (65)*

Any incident that directly or indirectly led, might have led or might lead to any of the following:

- (a) the death of a patient, user or other person,
- (b) the temporary or permanent serious deterioration of a patient's, user's or other person's state of health,
- (c) a serious public health threat *i.e.* an event which could result in imminent risk of death, serious deterioration in a person's state of health, or serious illness, that may require prompt remedial action, and that may cause significant morbidity or mortality in humans, or that is unusual or unexpected for the given place and time (Article 2 (66)).

14.2 Assessment of AE and SAEs

Each AE must be assessed for seriousness, causality, severity by the investigator or another suitably qualified physician in the research team who is trained in recording and reporting AEs.

The expectedness assessment will be performed by the sponsor.

The investigator and sponsor will make an assessment of seriousness (as defined above).

The investigator and sponsor will also make an assessment of the causal relationship with the study product, and/or associated products, and/or study procedures according to the following definitions:

1. **Not related:** where an event is not considered to be related to the study product and/or associated products and/or study procedures.
2. **Possibly related:** the relationship with the use of the investigational device or comparator, or the relationship with procedures, is weak but cannot be ruled out completely. Alternative causes are also possible (e.g., an underlying or concurrent illness/ clinical condition or/and an effect of another device, drug or treatment). Cases where relatedness cannot be assessed, or no information has been obtained should also be classified as possible.
3. **Probably related:** the relationship with the use of the investigational device or comparator, or the relationship with procedures, seems relevant and/or the event cannot be reasonably explained by another cause.
4. **Causal relationship:** the adverse event is associated with the investigational device, comparator or with procedures beyond reasonable doubt when:
 - the event is a known side effect of the product category the device belongs to or of similar devices and procedures;
 - the event has a temporal relationship with investigational device use/application or procedures;
 - the event involves a body-site or organ that:
 - o the investigational device or procedures are applied to;
 - o the investigational device or procedures have an effect on.
 - the adverse event follows a known response pattern to the medical device (if the response pattern is previously known);
 - the discontinuation of medical device application (or reduction of the level of activation/exposure) and reintroduction of its use (or increase of the level of activation/exposure), impact on the adverse event (when clinically feasible);
 - other possible causes (e.g., an underlying or concurrent illness/ clinical condition or/and an effect of another device, drug or treatment) have been adequately ruled out;
 - harm to the subject is due to error in use;

- the event depends on a false result given by the investigational device used for diagnosis when applicable.

The investigator will make an assessment of severity for each AE and this should be recorded on the eCRF according to the following categories:

- **Mild**: an event that is easily tolerated by the research participant, causing minimal discomfort and not interfering with every day activities;
- **Moderate**: an event that is sufficiently discomforting to interfere with normal everyday activities.
- **Severe**: an event that prevents normal everyday activities.

The term 'severe' used to describe the intensity of an event should not be confused with the term 'serious', which is a regulatory definition based on trial participant/event outcome action criteria. For example, a headache may be severe but not serious, while a minor stroke may be serious but is not severe.

14.3 Reporting of medical device cases

All AEs and DD that would occur during the 3-day follow-up period will be asked to be reported by the parents/guardians via the mobile application daily, whether they think it is related to the investigational device or not. The questionnaire to be used by the parents/guardians is provided in Table 3 above.

The questionnaire will be formulated such that the parents/guardians will be able to describe the AE to allow the determination of seriousness and causality by the investigator.

Following a declaration, an automatic notification will be sent to the investigator who will then be required to follow-up on the event.

The following would be defined as elements that could be a potential AE during the 3-day follow-up:

- Any new illness or symptom (diagnosed or undiagnosed);
- Any worsening of an existing illness or symptoms (diagnosed or undiagnosed);
- Any usual or unusual health-related event (such as loss of appetite, teething pain, reflux etc.).

Investigator's responsibility:

All these foreseeable events can be mitigated by carefully reading the IFU and by storing the device out of the reach of children and in suitable conditions as detailed in the IFU.

All AE, SAE and DD observed during the study must be reported in the eCRF by the investigator. Each AE must be assessed for seriousness, severity and causality by the investigator.

For AE or SAE including DD whether or not considered as related to the device or to the procedure the investigator will complete immediately and within 3 calendar days the form (FORM_CVI_6585) "Solicited adverse event collection form" and collect the results of the carried-out examinations and the reports of hospitalisation if applicable.

In case the investigator is aware of any new information, it should be reported to the sponsor.

Contractor's responsibility:

The contractor conducting the study will be required to provide the following information that has been brought to his attention about the investigational device within 1 business day after its acknowledgment in the eCRF:

- Any AE or SAE including DD which arises from the use of Petit Drill;
- Any SAE considered as related to the procedure of the study.

The safety information will be communicated to Pierre Fabre Vigilance department no later than 24 hours upon its reception by the contractor, through the form (FORM_CVI_6585) "Solicited adverse event collection form", which will be sent by email: [contact].

After completion of the study, newly occurring AEs potentially related to a Pierre Fabre product should be reported as spontaneous reports to the Pierre Fabre local vigilance department; a corresponding reporting form can be requested via the above contact data.

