6.3.2 Secondary outcome(s)

- SO1. Baseline clinical and sociodemographic characteristics of children will be summarized using descriptive statistics;

Secondary criteria related to the performance and the clinical benefit of Petit Drill will be described as follow:

- SO2. Score global and score of the 5 items of PCQ (Q1: cough frequency, Q2: sleep disturbance of the child, Q3: sleep disturbance of the parent, Q4: cough severity, Q5: degree of bothersomeness to the child) will be described after 1, 2 and 3 day-treatment with Petit Drill. The percentage of children with a 3 point-decrease of PCQ total score from baseline at 1 and 2 day-treatment with Petit Drill will be described;
- SO3. Daily cough severity will be measured using visual analogue scale (VAS) ranging from 0 (no cough) to 100 (worst cough) in response to "Yesterday, how was the cough of

my child during the day?", measured VAS after 1, 2 and 3 day-treatment with Petit Drill. the evolution of scores from baseline will be described;

•SO4. Scores of the Parent-proxy Children's Acute Cough-Specific Questionnaire PAC-QoL (global and dimensions) will be collected at baseline (D1) and after 3 day-treatment with Petit Drill (morning D4), or on the next morning of the last day of treatment. The evolution of scores from baseline will be described.

Secondary criteria related to the assessment of use and the safety of Petit Drill will be described as follow:

- SO5. The mean (SD) number of times Petit Drill was administered in each 24-hour period from the first (D1) to the third (D3) day of treatment initiation will be described;
- SO6. Parent's satisfaction with Petit Drill use will be described using a questionnaire, and responses measured using Likert scales. Responses will be presented as percentages;
- SO7. Safety will be assessed by the analysis of:
 - Adverse events (frequency, severity, emergence, and causal relationship of adverse events) tabulated according to IMDRF terms (International Medical Device Regulators Forum, Annex E). Number and percentage of relevant AEs during treatment with Petit Drill, defined as all SAEs or AEs related to the device, and any AEs of special interest;
 - Number and percentage of device deficiencies.

6.3.3 *Exploratory outcomes*

- SO8. The percentage of children receiving Petit Drill with or without physician prescription will be described by two age groups: from 6 months to 12 months old and from 13 months old to 6 years of age;

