For secondary safety outcome: number and percentage of AEs, including device deficiencies (DD) (to be completed by the investigator during an interview with the parent/legal representative)	Once a day, at a time of choice and at investigation end.	All AEs during the 3-day period will be asked to be reported by the patient, whether they think it is related to the investigational device or not. Once a day the following questions will be asked. 
• Today did your child experience any sort of illness or negative effects (whether related to the Syrup or not)? Yes/ No If yes, please contact the investigator.
		CONFIDENTIAL V6.0 #Sans suivi modifications#26-MAR-2024 Page 34/65

Pierre Fabre

CLINICAL INVESTIGATION PLAN (CIP)

Outcome	Suggested schedule	Variables
Adherence	At least once a day or at each intake	
How many times in the previous 24 hours did your child use Petit Drill? (Insert a single digit number)
 
For each dose, please give the approximate time: HH:MM
 
If Petit Drill is stopped before the recommended treatment duration of 3 days, please specify the reason:
 
Cough improvement / Cough worsening / Other /Other specify

Parent Satisfaction with Petit Drill Syrup Use	At study end (after 3 days of use)	
 How would you rate the quality of therapeutic management your child received? (Excellent/ Good/ Fair/ Poor) To what extent did this treatment meet your child's needs? (Almost all of my child's needs were met/ Most of my child's needs were met/ Only few of my child's needs were met/ None of my child's needs were met) Would you recommend this treatment to another parent? (No, definitely not/ Not really/ Yes, generally/ Yes, definitely) How satisfied are you with information received from the IFU to use this treatment? (Quite dissatisfied/ Indifferent or mildly dissatisfied/ Mostly satisfied/ Very satisfied) In a general sense, was it easy to use this treatment? (No, definitely not/ Not really/ Yes, generally/ Yes, definitely) Did your child seem to like the taste of the syrup? (No, definitely not/ Not really/ Yes, generally/ Yes, definitely)

Pierre Fabre

CLINICAL INVESTIGATION PLAN (CIP)

Table 4: Variables to be collected by the investigator in case of AE or DD occurring during patient follow-up

Outcome	Suggested schedule	Variables

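### Section 14.3 promises a daily request for device deficiencies, but the Table 3 question it relies on asks only about the child's health, so deficiencies without illness are not prompted for

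*Protocol*

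**What the plan says.** Section 14.3 says of AEs and DDs together: "All AEs and DD that would occur during the 3-day follow-up period will be asked to be reported by the parents/guardians". Reporting is to be daily, through the mobile application, and regardless of suspected cause. The section then names the instrument: "The questionnaire to be used by the parents/guardians is provided in Table 3 above".

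The safety row of Table 3 (Section 6.4) is labelled as covering DDs as well as AEs. Its schedule is "Once a day, at a time of choice and at investigation end". The one question shown begins "Today did your child experience any sort of illness or negative effects", adds that the cause does not matter, and tells a parent who answers yes to contact the investigator.

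The itemised list of device problems (packaging, cap, bottle, pipette, confusion over dosing or the instructions, accidental access) is in Table 4, whose title is "Variables to be collected by the investigator in case of AE or DD occurring during patient follow-up".

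SO7 in Section 6.3.2 includes "Number and percentage of device deficiencies" as a component, and Section 7.2 plans 95% confidence intervals for the secondary safety outcomes.

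**The concern.** The commitment in Section 14.3 and the instrument it cites do not match. Section 14.1.3 defines a DD broadly: use errors and inadequate manufacturer information count, and neither has to harm the child. A parent with a cracked pipette, or who misread the instructions, can truthfully answer no to a question about the child's health. Nothing then opens the Table 4 checklist.

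The numerator of the SO7 deficiency percentage would then depend on which parents volunteer a problem. The confidence interval reflects sampling error only, so a low count would look precise whether deficiencies were rare or simply not asked about. Near-misses matter most here. Note 2 of Section 14.1.2 treats as serious adverse events those deficiencies that could have led to one in less fortunate circumstances, and such events may leave the child well. Section 5.3 presents this as the first clinical investigation to yield clinical safety data on the product. Section 8.2.1 locks parent-reported data at study end with little room for later correction, so the analysis cannot recover what was not collected.

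**Working it through.** No figure in the protocol bears directly on this point, so the check is mainly a comparison of text.

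**1. What is promised against what is asked**

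| Place | AEs | DDs |
|---|---|---|
| Section 14.3 | asked for daily in the app | asked for daily in the app |
| Table 3, row label | covered | covered |
| Table 3, question shown | asked | no wording |
| Section 6.1, data that parents record in the app | listed | not listed |
| Section 8.1.2, content of the app | listed | not listed |
| Table 4, checklist | after an AE or DD is raised | after an AE or DD is raised |

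A DD is promised in Section 14.3 and in the row label, but the question itself never mentions one.

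**2. Routes that remain for a DD without illness**

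- Section 11: the parent records the details in the app, and the investigator is notified and makes contact.
- Table 4: it may be completed at any time during follow-up, and a DD alone is enough to open it.

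Both start with the parent raising the problem unprompted. For AEs, Section 6.10 also asks parents to tell the investigator as soon as possible.

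**3. Recall period**

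The safety question covers *today* and is answered once a day at a time the parent chooses. Read literally, an event after the answer falls outside that answer and outside the next day's *today*. The adherence item in the same table asks about the previous 24 hours, and PAC-QoL also uses a 24-hour recall.

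Illustration only, because the answering time is an assumption: with an answer at hour *h*, the share of the calendar day left unprompted is (24 − *h*)/24.

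- 08:00: 16/24 = 67%
- 12:00: 12/24 = 50%
- 18:00: 6/24 = 25%
- 22:00: 2/24 = 8%

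These are hours outside a literal reading of the question. They are not a share of events lost.

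**4. What an interval would show if no DD were reported**

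The protocol's sample size reproduces: 1.96² × 0.5 × 0.5 / 0.07² = 195.99, rounded up to 196, and 196 / 0.80 = 245. For zero events in *n* children, the exact (Clopper-Pearson) two-sided 95% upper limit is 1 − 0.025^(1/*n*):

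- *n* = 245: 1.49%
- *n* = 196: 1.86%

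The zero count is hypothetical. It shows only that the interval would look equally reassuring whether or not parents had been asked.

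**The case against.** The strongest objection is that a reader might infer that deficiencies, and events later in the day, are simply missed. The documents do not support that. Section 11 gives parents an app route for DDs with notification of the investigator, Section 6.10 asks for prompt reporting of any AE, and Table 4 is open throughout follow-up. The Table 3 row also states that AEs over the whole 3-day period are to be reported, and it repeats the question at investigation end. This stands: the supportable claim is lack of a prompt and possible under-reporting.

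A second objection is that the Table 3 row says the investigator completes it in an interview, where a DD could come up. But the question tells the parent to make contact after a yes, so as written the interview follows a positive answer. A parent whose only problem is with the device has no reason to give one.

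Third, parents are asked at study end about ease of use and satisfaction with the instructions, and the adherence item records the number and times of doses. Some use problems would therefore be visible. These items serve SO5 and SO6, do not capture a wrong volume or a damaged component, and do not open the DD checklist.

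Fourth, the wording may not be final: the schedule column is headed as suggested, and Section 14.3 says the questionnaire is still to be formulated so that parents can describe an AE. That is a fair caution, and it also makes the correction easy. It does not remove the mismatch, since Section 14.3 cites Table 3 as the instrument.

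Finally, a reader might turn the recall gap into a percentage of follow-up not covered. Any such figure depends on assumed clock times and on a strict reading of *today*, so it cannot measure loss.

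**Conclusion.** The mismatch on DDs holds, with high confidence. Section 14.3 commits to asking for them daily, and the cited question does not. Followed as written, the deficiency count and percentage in SO7 rest on unprompted reports and may be too low. The size of any shortfall cannot be derived from the protocol. The conclusion assumes that the app carries the Table 3 wording as shown.

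The recall period is a lesser, literal-wording point. It stands because the adherence item in the same table already uses a 24-hour look-back, but the immediate-reporting instruction and the end-of-study repeat soften it. The repeat closes little of the gap if it keeps the same *today* wording.

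The primary outcome and the sample size are unaffected. The change is worth making because it concerns what is collected, and the statistical analysis plan cannot repair that afterwards.

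**What to change.** Reconcile Section 14.3 with Table 3:

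1. Add one daily Yes/No item on whether there was any problem with the bottle, the pipette, the dosing or the instructions.
2. Make the safety question cover the time since the last entry, or the previous 24 hours as the adherence item does. Have the question at investigation end cover the whole follow-up.
3. Show the existing Table 4 deficiency checklist once to every parent at the final entry, whether or not anything has been reported.
4. Add DDs to the app content listed in Sections 6.1 and 8.1.2.

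The cost is a change to the app wording, one extra item and one checklist, or about a minute more per parent. No extra children or visits are needed. Section 12.2 submits the data collection tools to the ethics committee, so the change may need an amendment. More minor DDs will probably be reported, and the report should say that they were solicited.
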